9.9.2.1. Renal Artery Stenosis Evaluation at 12 Months

With an expected rate of 3.1% for renal artery stenosis at 12 months [7], a sample size of 50 subjects will provide a 95% confidence interval of approximately (0.5%, 13.7%) using the exact method (calculated using an event rate of $2/50=4\%$).

Descriptive statistics of this endpoint at 12 months will be provided using counts, percentages and the 95% confidence interval.

9.9.3. Primary Efficacy Endpoint

The primary efficacy endpoint of the study is the baseline adjusted (ANCOVA) change in SBP from baseline (SV2) to 6-months post-procedure as measured by 24-hour ABPM.

In the context of an ANCOVA linear regression model, $\mu = \mu_t - \mu_c$ represents the baseline-adjusted treatment effect of BP change comparing RDN and control groups where μ_t and μ_c are the baseline adjusted BP changes in the RDN and control groups respectively. Let $\mathbf{y} = \{\mathbf{y}_t, \mathbf{y}_c\}$ and $\mathbf{y}_0 = \{\mathbf{y}_{0t}, \mathbf{y}_{0c}\}$ represent the prospective data and prior data respectively, where $t = \text{RDN group}$ and $c = \text{control group}$. Let the hypotheses for the study be the following:

$$H_0: \mu = 0$$

$$H_a: \mu < 0$$

We reject H_0 if the probability is greater than 97.5%, i.e.

$$P(\mu < 0 | \mathbf{y}, \mathbf{y}_0, \hat{\varrho}(\mathbf{y}, \mathbf{y}_0, \lambda, k)) > 0.975$$

where the notation $\hat{\varrho}(\mathbf{y}, \mathbf{y}_0, \lambda, k)$ is used to denote that the estimate of ϱ depends on the prospective data, prior data, and the Weibull shape and scale parameters. In conjunction with a pre-specified decision rule controlling the prior data weight, the estimate of $\hat{\varrho}(\mathbf{y}, \mathbf{y}_0, \lambda, k)$ represents a measure of similarity between prospective and prior data. Alternatively, in the absence of $\hat{\varrho}(\mathbf{y}, \mathbf{y}_0, \lambda, k)$, i.e., $P(\mu < 0 | \mathbf{y}, \mathbf{y}_0)$, full weight would be given to the prior data.

9.9.4. Primary Efficacy Endpoint Analysis

The primary analysis of the powered primary endpoint will be performed using Bayesian methods as outlined in this section. The Bayesian posterior treatment effects will be determined along with the 95% Bayesian Credible Interval (BCI). The ITT population will be used as the primary analysis population for this endpoint. Secondary Bayesian effectiveness analyses will also be performed using the modified ITT, per-protocol and as-treated populations defined in section 9.1.3.

The power prior discount function approach is used to estimate μ , and determine $\hat{\varrho}(\mathbf{y}, \mathbf{y}_0, \lambda, k)$, the strength of the prior data used to estimate μ . $\hat{\varrho}(\mathbf{y}, \mathbf{y}_0, \lambda, k)$ ranges from 0 to 1, where 1 means that 100% of the prior data is used and 0 means that no prior data is used. Before beginning the study, an initial value is chosen for $\hat{\varrho}(\mathbf{y}, \mathbf{y}_0, \lambda, k)$, call this value α_{max} . This α_{max} value is the maximum strength the prior data can receive. We intend to use the same enrollment criteria for the prior and prospective studies, and therefore believe that a value of $\alpha_{max} = 1$ is appropriate.

At interim looks and at the final analysis, we analyze the data using the power prior discount function method, this method will discount α_{max} to an appropriate value $\hat{\varrho}(\mathbf{y}, \mathbf{y}_0, \lambda, k)$ where $\hat{\varrho}(\mathbf{y}, \mathbf{y}_0, \lambda, k) \leq \alpha_{max}$. This discounting is based on the discount function which is discussed in detail in the next section.

Under the adaptive procedure, if the prospective data diverges from the prior data at an interim look, the discount function will discount the strength of the prior data, thus requiring continued enrollment to maintain power to achieve the endpoint. Alternatively, if the prior and prospective data agree, there will be a smaller penalty from the discount function, thus fewer prospective patients would be needed to maintain power.

9.9.4.1. Discount Function Estimation Method

The power prior discount function method is comprised of four steps: **Compare, Discount, Combine, and Estimate.**

Compare:

We start by stochastically comparing prospective data vs prior data as follows,

For each treatment group, we separately fit the model to the combined prior and pivotal data:

$$y_i = \beta_0 + \beta_1 I(i \in \text{prior}) + \beta_2 x_i + \varepsilon_i, \quad \varepsilon_i \sim N(0, \tau^2),$$

where $I(i \in \text{prior}) = 1$ if the subject is from the prior dataset, and 0 otherwise, y_i is the BP change for the i th observation and x_i is the mean centered baseline BP for the i th observation. With flat priors on

each parameter, we estimate the posterior probability that $\beta_1 > 0$ by first computing, using Monte Carlo sampling

$$p^* = P[\tilde{\beta}_1 > 0 \mid \mathbf{y}, \mathbf{y}_0].$$

Having calculated this separately for both the RDN (p_t^*) and control groups (p_c^*), they are transformed to p_t and p_c using

$$p = \begin{cases} 2p^*, & p^* \leq 0.5 \\ 2(1 - p^*), & p^* > 0.5 \end{cases}$$

Now, under this transformation, if p_t or p_c are close to 0, there is a high probability that the prospective data and prior data come from different populations and discounting should be applied to reduce the influence of the prior. On the other hand, if p_t or p_c are close to 1, there is a high probability that the prospective data and prior data come from similar populations and minimal discounting should be applied.

Discount:

[figure not shown]
We discount α_{max} based on the value of p_t and p_c from the **Compare** step and the discount function $F(p)$,

$$\hat{\alpha} = \alpha_{max}F(p),$$

where $F(p)$ is a function between 0 and 1. A two-sided Weibull function will be utilized as follows:

$$F(p) = 1 - e^{-\lambda p^k}$$

For this study, we will be using a shape parameter of $k = 3$ and a scale parameter of $\lambda = 0.25$ (illustrated below). Note that we will use the same Weibull function parameters for both RDN group and control group, but p_t and p_c will have different values from the **Compare** step.

Combine:

Using the power prior method and $\hat{\theta}$ we can combine the prior and prospective data together using Bayesian techniques to construct the posterior distribution for μ as follows. We first begin with a hierarchical linear regression model of the form:

$$\begin{aligned} y_i | \mu_t, \mu_c, \beta, \sigma^2 &\sim N(\mu_t I(i \in t) + \mu_c I(i \in c) + x_i \beta, \sigma^2), i = 1, \dots, n, \\ \mu_t | \mu_{0t}, \sigma_{0t}^2, \hat{\alpha}_t &\sim N(\mu_{0t}, \sigma_{0t}^2 / \hat{\alpha}_t), \\ \mu_c | \mu_{0c}, \sigma_{0c}^2, \hat{\alpha}_c &\sim N(\mu_{0c}, \sigma_{0c}^2 / \hat{\alpha}_c), \\ \beta &\sim N(a_\beta, b_\beta^2), \\ \pi(\sigma^2) &\propto \sigma^{-2}, \end{aligned}$$

where $N(\cdot)$ denotes a normal distribution, $I(\cdot)$ is the indicator function where $I(i \in t)$ indicates that observation i is in the RDN group and $I(i \in c)$ indicates observation i is in the control group, y_i is the BP change for the i th observation, x_i is the mean centered baseline BP value for the i th observation, and each of $\mu_{0t}, \mu_{0c}, \sigma_{0t}^2, \sigma_{0c}^2$ are hyperparameters estimated from the historical data, and $a_\beta = 0$ and $b_\beta = 10^{10}$.¹⁰

To carry out estimation in a computationally efficient manner, we rely on a reparameterization derived in Gelman [4]. First, construct vectors and matrices: $\mathbf{y} = (y_1, \dots, y_n)^T$, \mathbf{x}_t and \mathbf{x}_c vectors of binary treatment control indicators taking values 0 and 1, \mathbf{x}_β the vector of mean centered baseline values, $\mathbf{X} = (\mathbf{x}_t | \mathbf{x}_c | \mathbf{x}_\beta)$ the $n \times 3$ design matrix, and $\boldsymbol{\theta} = (\mu_t, \mu_c, \beta)^T$ parameters of interest to be estimated. Then, we can write the model as

$$\mathbf{y}_* \sim N(\mathbf{X}_* \boldsymbol{\theta}, \boldsymbol{\Sigma}_*),$$

where $\mathbf{y}_* = (\mathbf{y}^T, \mu_{0t}, \mu_{0c}, a_\beta)^T$, $\mathbf{X}_* = (\mathbf{X}^T, \mathbf{I}_3)^T$, \mathbf{I}_3 is a 3×3 identity matrix, and

$$\boldsymbol{\Sigma}_* = \begin{pmatrix} \sigma^2 \mathbf{I}_n & 0 \\ 0 & \boldsymbol{\Sigma}_\theta \end{pmatrix},$$

where

$$\boldsymbol{\Sigma}_\theta = \begin{pmatrix} \sigma_{0t}^2 / \hat{\alpha}_t & 0 & 0 \\ 0 & \sigma_{0c}^2 / \hat{\alpha}_c & 0 \\ 0 & 0 & b_\beta^2 \end{pmatrix}.$$

The posterior mean of $\boldsymbol{\theta}$ is found via least squares as

$$\hat{\boldsymbol{\theta}} = (\mathbf{X}_*^T \boldsymbol{\Sigma}_*^{-1} \mathbf{X}_*)^{-1} \mathbf{X}_*^T \boldsymbol{\Sigma}_*^{-1} \mathbf{y}_*,$$

and the posterior variance of $\boldsymbol{\theta}$ is

$$\mathbf{V}_\theta = (\mathbf{X}_*^T \boldsymbol{\Sigma}_*^{-1} \mathbf{X}_*)^{-1}.$$

Thus, the posterior distribution of $\boldsymbol{\theta}$ is $\boldsymbol{\theta} | \mathbf{y}_*, \boldsymbol{\Sigma}_* \sim N(\hat{\boldsymbol{\theta}}, \mathbf{V}_\theta)$. Both $\hat{\boldsymbol{\theta}}$ and \mathbf{V}_θ are composed of an unknown σ^2 . The marginal posterior distribution of σ^2 is

¹⁰ In the R package bayesDP version 1.3.2, the bdplm function parameter ‘prior_covariate_sd’ is described as “The prior standard deviation(s) of the covariate effect(s). Default value is 1e4.” Upon inspection of the code, it appears the standard deviation is internally scaled by 1e6, thus yielding a more diffuse prior for β . Therefore, the actual value of b_β used in the analysis is 1e10.

$$q(\sigma^2 | \mathbf{y}) \propto \pi(\sigma^2) |\sigma^2 \mathbf{I}_n|^{-\frac{1}{2}} \exp \left\{ -\frac{1}{2} (\mathbf{y}_* - \mathbf{X}_* \boldsymbol{\theta})^T \Sigma_*^{-1} (\mathbf{y}_* - \mathbf{X}_* \boldsymbol{\theta}) \right\},$$

which does not have a known distributional form. Here, $\pi(\sigma^2)$ is the prior distribution of σ^2 . Thus, to draw samples from the posterior distribution of σ^2 , we rely on a grid search to sample values of σ^2 .

We proceed by drawing samples from $\sigma^2 \sim q(\sigma^2 | \mathbf{y})$. Using these estimates, we input them into the posterior distribution of $\boldsymbol{\theta}$. By repeating this process, a large number of times, we will be drawing posterior samples from $\boldsymbol{\theta}$ which will account for the uncertainty in both σ^2 as well as appropriately weighting the prior data based on $\hat{\alpha}_t$ and $\hat{\alpha}_c$.

We can then construct the following contrast of interest from the drawn samples:

$$\mu = \mu_t - \mu_c.$$

Use of this contrast leads to the univariate distribution of interest concerning the mean BP change difference between the RDN and control groups.

[figure not shown]
Estimate:

The posterior distribution from the combined prior and prospective data is used to estimate the posterior probability

$$P(\mu < 0 | \mathbf{y}, \mathbf{y}_0, \hat{\alpha}(\mathbf{y}, \mathbf{y}_0, \lambda, k)) \quad (1)$$

where the notation $\hat{\alpha}(\mathbf{y}, \mathbf{y}_0, \lambda, k)$ is used to denote that the estimate of α depends on the prospective data, prior data, and the Weibull shape and scale parameters. In conjunction with a pre-specified decision rule controlling the prior data weight, the estimate of $\hat{\alpha}(\mathbf{y}, \mathbf{y}_0, \lambda, k)$ represents a measure of similarity between prospective and prior data. Alternatively, in the absence of $\hat{\alpha}(\mathbf{y}, \mathbf{y}_0, \lambda, k)$, i.e., $P(\mu < 0 | \mathbf{y}, \mathbf{y}_0)$, full weight would be given to the prior data.

[figure not shown]
The blue dashed line in the figure below is an illustrative example of the estimate from prospective data (black) and prior data (red).

The analysis in (1) is performed at all interim looks and at the final analysis.

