The prior data consists of the first consecutively randomized 80 subjects in the SPYRAL HTN-ON MED study, which were randomized in a 1:1 ratio to RDN or control. The results from these 80 subjects have already been analyzed and published [6].

The prospective data consists of the following two cohorts:

[figure not shown]
1. Subjects 81 to 106 which have already been enrolled and were randomized in a 1:1 ratio to RDN vs. control, and whose data has not been unblinded and analyzed by Medtronic.
2. All remaining subjects in the SPYRAL HTN-ON MED Study from 107 onwards which will be randomized in a 2:1 ratio to RDN vs control.

The weight of the prior data will be adjusted using a discount function, which scales from 0 to 1, according to the similarity of the prior and prospective data. The discount function adjusts the amount of weight the prior receives. This prevents the use of an informative prior where exchangeability issues are present (e.g., the prior and prospective data are quite different). This discount function approach was proposed by the Medical Device Innovative Consortium (MDIC) working group and is a collaborative

effort between FDA and industry through the MDIC [1,2]. If the analyses show a high level of agreement for prospective data compared to the prior, the prior will be weighted at or near 100%. If the prospective data perform much worse than or much better than the prior, then the prior will receive very little or zero weight. The Bayesian adaptive design is set up to enroll patients until a sufficient sample size is achieved to have high probability of meeting the endpoint.

The sample size of the study will vary from a minimum of 110 to 221 subjects with evaluable data due to the adaptive nature of the trial. This will require approximately 130 to 260 randomized subjects assuming a 15% rate of attrition at 6-months.

- The first interim analysis will take place when we have a minimum of 110 subjects with evaluable data. With an expected attrition rate of 15%, this will require approximately 130 randomized subjects. If the attrition rate is higher than 15%, then additional subjects will be randomized in order to reach a minimum of 110 evaluable subjects.

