9.9.4.2. Illustration of Discount Function Scenarios

The Figure below shows how the discount function operates with hypothetical data sets

The panels in this figure can be interpreted as follows:

- **Top panel:** The prospective (current) data is very similar to the prior. The discount function allows for full strength of the prior. The posterior (final estimate) is a balance between the prior and prospective study.
- **Middle panel:** The prospective (current) data is similar to the prior. The discount function penalty is moderate, resulting in a prior effective sample size of 17 out of a max of 50. Because the agreement is reasonable, the posterior (final estimate) is similar to both the prior and prospective study.
- **Bottom panel:** The prospective (current) data shows lower performance than the prior. The discount function produces a substantial penalty resulting in no weight to the prior. The posterior (final estimate) is essentially the same as the prospective (current) estimate.

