9.9.4.3. Simulation of Primary Efficacy Endpoint Operating Characteristics

Simulations were performed to assess operating characteristics for the primary efficacy endpoint and are presented in the two tables below. We used 8000 trial simulations to estimate the power and 15000 simulations to estimate the type I error. The overall power for the primary efficacy endpoint from **Table 4** is 96%, with a one-sided type I error rate of 0.038.

Table 3: Simulation Parameters for Primary Efficacy Endpoint

Prior Baseline Adjusted RDN Group Mean (SE)	-8.85 (1.75) mmHg
Prior RDN Group N	36
Prior Baseline Adjusted Control Group Mean (SE)	-1.80 (1.75) mmHg
Prior Control Group N	36

Maximum Prior Patients	36 + 36 = 72 (out of 80)
Prospective Study Expected Treatment Difference	-5.0 mmHg
Prospective Study RDN Group Mean (SD)	-6.8 (12) mmHg
Prospective Study Control Group Mean (SD)	-1.8 (12) mmHg
Weibull Discount Function Parameters	Shape: $k = 3$, Scale: $\lambda = 0.25$
Attrition rate at 6-months	15%

Table 4: Study Operating Characteristics for Primary Efficacy Endpoint

Trial Success Rate (Power)	96%
Type I Error	0.038
First Interim Look N	N=110 evaluable (~130 randomized)
Power at First Interim Look	83%
Second Interim Look N	N=149 evaluable (~175 randomized)
Power at Second Interim Look	91%
Maximum Study Size	N=221 evaluable (260 randomized)
% of Simulations that Stop for Futility	1.71%

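### The printed discount function caps the prior weight at 22%, contradicts the stated borrowing rule and does not reproduce the power in Table 4

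*SAP*

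**What the plan says.** SAP section 9.9.4.1 (Discount step) multiplies alpha_max by a Weibull function of the agreement measure p, printed as "F(p) = 1 - e^{-\lambda p^k" with the exponent closed after k. It sets a "shape parameter of $k = 3$ and a scale parameter of $\lambda = 0.25", and Table 3 in section 9.9.4.3 lists the same values for the simulations: "Shape: $k = 3$, Scale: $\lambda = 0.25". Section 9.9.4 holds that a "value of $\alpha_{max} = 1$ is appropriate" and describes the weight as running from 0 to 1, "where 1 means that 100% of the prior data is used and 0 means that no prior data is used".

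The text says what this function should do when the data agree. Section 8 states that with high agreement "the prior will be weighted at or near 100" percent. The Compare step of 9.9.4.1 asks for minimal discounting when p is close to 1. The top panel in 9.9.4.2 is described with the words "The discount function allows for full strength of the prior".

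Table 4 reports 83% under "Power at First Interim Look", 91% at the second look and 96% overall, with 1.71% of simulations stopping for futility and a type I error of 0.038.

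**The concern.** With lambda = 0.25 multiplying p^k, the exponent never goes below -0.25, so the function cannot come near 1. The printed formula would discard most of the prior in every case, including perfect agreement. That is the opposite of what the text promises, and it removes most of the borrowing on which the sample size rests. Calling lambda a scale parameter points to a different expression, in which p is divided by lambda.

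The function is applied at both interim looks and at the final analysis, so it affects the posterior probability compared with 0.975 and the predictive calculation for futility. Section 9.8 gives the Bayesian analyses to an independent organization, and section 10 requires independent validation of the primary endpoint programming. Anyone who codes 9.9.4.1 literally would obtain a different posterior and possibly a different stopping decision. Sensitivity analysis 9.9.5.1 reuses the same function and inherits the problem.

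**Working it through.** **Inputs.** k = 3, lambda = 0.25 (9.9.4.1 and Table 3). alpha_max = 1 (9.9.4). Prior means -8.85 (RDN) and -1.80 (control), each with SE 1.75 and n = 36; prospective means -6.8 and -1.8 with SD 12 (Table 3). Looks at 110, 149 and 221 evaluable (Table 4). Success if P(mu < 0) > 0.975 (9.9.3).

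Allocation: subjects 81 to 106 are 1:1 and later subjects 2:1 (section 8). With 15% attrition the first 26 give about 22 evaluable (11/11), and the remainder splits 2:1. The arm sizes (RDN/control) are therefore about 70/40, 96/53 and 144/77.

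**Step 1: the function itself.** Printed form: 1 - exp(-0.25 p^3). Scale form: 1 - exp(-(p/0.25)^3).

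| p | Printed | Scale form |
|---|---|---|
| 0.25 | 0.004 | 0.632 |
| 0.50 | 0.031 | 0.9997 |
| 0.75 | 0.100 | 1.000 |
| 1.00 | 0.221 | 1.000 |

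The printed maximum corresponds to 0.221 × 36 = 8.0 prior subjects per arm.

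**Step 2: which form reproduces Table 4.** The design was simulated with 20,000 trials per form: per-arm comparison p under flat priors, weight F(p), normal prior with variance SE²/weight in each arm, and predictive futility at both interims. Cumulative success and futility stops:

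| | Look 1 | Look 2 | Final | Futility stops |
|---|---|---|---|---|
| Table 4 | 83% | 91% | 96% | 1.71% |
| Scale form | 83% | 91% | 96% | 1.4% |
| Printed form | 58% | 73% | 86% | 5.1% |

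Mean first-look weights were 0.72 (RDN) and 0.90 (control) under the scale form, and 0.04 and 0.08 under the printed form.

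**Step 3: hand checks.**

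- *No borrowing, look 1.* SE = 12 × sqrt(1/70 + 1/40) = 2.38, so power = Phi(5/2.38 - 1.96) = Phi(0.14) = 56%. The printed form's 58% is barely above this.
- *Weight fixed at the cap in both arms, look 1.* Prior variance = 1.75²/0.221 = 13.8 per arm; data variances are 144/70 = 2.06 and 144/40 = 3.60. Posterior variances are 1.79 and 2.86, so the posterior SD of the difference is 2.16. The expected posterior difference is -5.27 (RDN mean -7.07, control -1.80) and its sampling SD is 1.96. Success needs a difference below -1.96 × 2.16 = -4.23, so power = Phi((5.27 - 4.23)/1.96) = Phi(0.53) = 70%. Simulation at this fixed weight gives 70%, 82% and 92%. Even with the maximum weight in every trial, 83% is not reached.

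**Step 4: other explanations tried for the printed form.** All 2:1 allocation gives 56/72/86%; all 1:1 gives 61/76/89%. Using SD 10.5 (1.75 × sqrt(36)) instead of 12 gives 69/83/93%. A third reading, 1 - exp(-p^k/lambda), has F(1) = 1 - exp(-4) = 0.98 but gives only about 71/83/93% (run without the futility rule). None matches Table 4.

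**The case against.** The equation was machine-read from a PDF, and the same reading garbles the discount symbol elsewhere. A lost fraction or bracket in the exponent cannot be excluded, and the plotted curve that would settle it is not shown. This stands as a caveat: the equation and curve should be checked in the source file. Nothing shows, however, that this particular equation was altered.

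The SAP also ties the analysis to a named version of the bayesDP package, so the sponsor's run is probably not coded from this line, and Table 4 itself appears correct. On that view this is a notation error, and the power losses would arise only if someone implemented the printed form. That is fair, and it is why the point should not be read as an underpowered design. It does not remove the error. The SAP must state the function that is applied, independent validation is required, and footnote 10 already reconciles text with package code for another parameter.

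The panels in 9.9.4.2 are hypothetical and state no Weibull parameters, so they are only supporting evidence.

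Type I error does not discriminate well. With both prospective means at -1.8 the scale form gave 0.040 and the printed form 0.045, against 0.038 stated. Table 3 does not give the null means, and the scale form is sensitive to them: 0.110 with both means at -3.5, against 0.050 for the printed form. The conclusion does not rest on these figures.

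**Conclusion.** The concern holds. As printed, the function limits the prior weight to 22.1%, contradicts section 8, the Compare step and the labelling of lambda as a scale, and falls short of Table 4 by 25 points at the first look (83 - 58), 18 at the second (91 - 73) and 10 overall (96 - 86). The cap is pure arithmetic and needs no assumption beyond p ≤ 1 and alpha_max = 1. The power figures take SD 12 as the residual SD, omit the baseline covariate draw and use approximate arm sizes. The scale form matches Table 4's power at all three looks under the same simplifications. The sponsor's simulations therefore appear to have used 1 - exp(-(p/lambda)^k), and the equation in 9.9.4.1 is what is wrong. Because it defines the primary analysis and both stopping decisions, it must be corrected.

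**What to change.** Check the code and the plotted curve, then replace the equation in 9.9.4.1 by F(p) = 1 - exp(-(p/lambda)^k) with k = 3 and lambda = 0.25. Add check values for programmers: F(0.1) = 0.06, F(0.25) = 0.63, F(0.5) > 0.99. Point 9.9.5.1 to the same expression.

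If the sponsor does intend the printed form, then the borrowing statements in section 8 and the power and futility entries in Table 4 must be restated from new simulations. Power would be about 58%, 73% and 86%. In either case, state the null means behind the type I error; no replacement value should be entered without them.

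If the code already uses the scale form, the cost is one equation and a few check values, and the analysis does not change. If the code uses the printed form, the change is substantive: mean first-look weights rise from 0.04 and 0.08 to 0.72 and 0.90, and the operating characteristics must be confirmed for whichever form is kept.

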9.8.3. Futility imputation procedure

For the futility calculation, we calculate the probability of futility based on the maximum study size of 260 randomized subjects which means we have three types of subjects to consider:

1. Subjects who have reached their 6-month endpoint.
2. Subjects who are enrolled and have baseline blood pressure but have not reached their 6 month endpoint.
3. Subjects who have not been enrolled.

Imputation procedures will be used to impute the blood pressure change for subjects of type 2 and type 3 above.

For type 2 subjects we use the following procedure:

- 2.1 Construct the posterior predictive distribution for blood pressure change using type 1 subjects, incorporating the prior data.
- 2.2 Simulate samples from the predictive distribution to impute the missing values of blood pressure change for type 2 subjects, conditional on observed baseline blood pressure.

For type 3 subjects, we do the following:

- 3.1 Construct the posterior predictive distribution for blood pressure change using type 1 subjects, including the prior data.
- 3.2 Simulate baseline blood pressure for type 3 patients.
- 3.3 Simulate blood pressure change from the predictive distribution.
- 3.4 Impute blood pressure change for type 3 subjects, conditional on simulated baseline blood pressure.

We then combine the type 1 subjects with the imputed subjects from steps 2.2 and 3.4 into a single dataset and construct the endpoint using the BayesDP function. This procedure will be repeated for many datasets ($N_{rep} = 1000$) and we calculate the number of times the alternative hypothesis is accepted. If the proportion of times the alternative hypothesis is accepted is less than 5%, stop enrollment due to futility.

We will use v1.3.2. of the bayesDP package, available on the Comprehensive R Archive Network (CRAN) [<https://CRAN.R-project.org/>].

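### The formula printed as the marginal posterior of σ² is not that marginal: it lacks the factor |V_θ|^(1/2), a minor error to correct and check against the code

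*SAP*

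**What the plan says.** Section 9.9.4.1 (Combine) gives θ = (μ_t, μ_c, β), conditional on σ², a normal posterior with mean θ̂ and variance V_θ. It notes that both of these "are composed of an unknown σ^2". It then announces a density for σ² with the words "The marginal posterior distribution of σ^2 is". In plain notation the printed kernel is

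`π(σ²) · |σ² I_n|^(-1/2) · exp{ -½ (y* - X*θ)' Σ*⁻¹ (y* - X*θ) }`.

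The exponent carries θ without a hat, and no determinant of V_θ appears. The SAP adds that this density is one "which does not have a known distributional form", and so "we rely on a grid search to sample values of σ^2". Each drawn σ² is put into the normal posterior of θ, and the contrast μ = μ_t − μ_c is formed from the draws.

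The result feeds the success rule of section 9.9.3, "We reject H_0 if the probability is greater than 97.5"%, at both interim looks and the final analysis. For software, section 9.8.3 says "We will use v1.3.2. of the bayesDP package", and footnote 10 to section 9.9.4.1 refers to that package's `bdplm` function.

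**The concern.** A marginal density of σ² cannot contain θ. Integrating θ out also leaves behind |V_θ|^(1/2). Because V_θ depends on σ², as the SAP itself says, a proportionality sign cannot absorb that factor.

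Leaving it out while plugging in θ̂ ignores the degrees of freedom spent on the three coefficients. The posterior for σ² then sits too low, the credible interval for μ is too short, and the probability compared with 0.975 is slightly too favourable. The formula belongs to the primary efficacy analysis, and section 10 requires independent validation of primary endpoint programming. A validator working from the printed text would either code a wrong density or fail to match the main program.

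**Working it through.** **1. The correct marginal.** Divide the joint posterior by the conditional, p(σ² | y) = p(θ, σ² | y) / p(θ | σ², y), and evaluate at θ = θ̂(σ²). The normal conditional has height proportional to |V_θ|^(-1/2) there. Hence

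`q(σ² | y) ∝ π(σ²) · |σ² I_n|^(-1/2) · |V_θ|^(1/2) · exp{ -½ (y* - X*θ̂)' Σ*⁻¹ (y* - X*θ̂) }`.

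The determinant of the prior block Σ_θ does not involve σ² and drops out.

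**2. Which reading of the printed form fits the text.** With θ held fixed, the prior part of the quadratic is constant in σ². With π(σ²) ∝ 1/σ², the kernel is then inverse-gamma(n/2, SSR/2), a standard form that needs no grid. The SAP says the form is unknown and uses a grid, draws σ² before θ, and feeds no draw of θ back. That fits θ̂(σ²) in the exponent, the reading under which the missing factor matters.

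**3. Size without borrowing (closed form).** With flat priors |V_θ|^(1/2) is proportional to (σ²)^(3/2). The correct form gives σ² ~ IG((n−3)/2, RSS/2), so μ has a t distribution on n−3 df with scale based on RSS/(n−3). Omitting the factor gives IG(n/2, RSS/2), so t on n df with scale based on RSS/n.

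- Ratio of posterior SDs: √[(n−5)/(n−2)].
- Single-look one-sided size of the 0.975 rule: P(t_{n−3} > t_{.975,n} · √[(n−3)/n]).

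| n (Table 4) | SD ratio | SD too small by | cut-off | size (correct form 0.0250) |
|---|---|---|---|---|
| 110 | √(105/108) = 0.9860 | 1.4% | 1.9818 × √(107/110) = 1.9546 | 0.0266 |
| 149 | √(144/147) = 0.9897 | 1.0% | 1.9760 × √(146/149) = 1.9560 | 0.0262 |
| 221 | √(216/219) = 0.9931 | 0.7% | 1.9708 × √(218/221) = 1.9573 | 0.0258 |

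The 95% interval width ratios are the same to three decimals.

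**4. Size with borrowing.** Inputs from Table 3: prior means −8.85 and −1.80, each with SE 1.75; prospective means −6.8 and −1.8, SD 12. Assumed evaluable splits RDN:control are 70:40, 95:54 and 144:77, from section 8's 1:1 allocation for subjects 81–106 and 2:1 thereafter. Integrating over a σ² grid with both prior weights equal to 1, the SD ratio is 0.9951, 0.9956 and 0.9963, so 0.5%, 0.4% and 0.4% too small. With only the control prior borrowed, it is 0.9913, 0.9933 and 0.9952, so 0.9%, 0.7% and 0.5%.

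**5. The plan's own operating characteristics.** Table 4 gives power of 83%, 91% and 96% by look, type I error 0.038 and 1.71% futility stops. A simplified simulation without the covariate, but with the 5% futility rule, used 8,000 trials under the alternative and 30,000 under the null. Both null means were set at −1.8 (an assumption).

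| | SAP Table 4 | correct density | factor omitted |
|---|---|---|---|
| Power, cumulative by look | 83 / 91 / 96% | 82.8 / 91.1 / 96.5% | 82.5 / 91.4 / 96.5% |
| Futility stops | 1.71% | 1.4% | 1.65% |
| Type I error | 0.038 | 0.039 | 0.040 |

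The Monte Carlo SE of the type I error is about 0.001, so the table cannot show which density was coded. These runs take the discount function as the Weibull CDF with scale 0.25, 1 − exp{−(p/0.25)³}, which is the reading that reproduces Table 4.

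A fuller ANCOVA simulation applied both densities to the same simulated data, without futility stopping. Type I error went from 0.0447 to 0.0457, and power was 97.0% either way. With no borrowing at all, the corresponding change was 0.0495 to 0.0519.

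**The case against.** A reader might infer that the trial's credible intervals are too narrow and that its 0.975 rule is anti-conservative. The documents do not support that as a fact. It follows only if the running code both plugs in θ̂ and omits the determinant, and the bayesDP code is not in the documents.

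The strongest counter-argument is that the printed kernel is the correct full conditional of σ² given θ. Iterated with drawn values of θ in a Gibbs sampler, it narrows nothing. In one check at n=110 the Gibbs SD was 1.934 against a correct 1.940 (prior weight 0.22) and 1.585 against 1.581 (weight 1), while omitting the factor gave 1.919 and 1.572. The mathematics stands, but the SAP describes no such iteration: it calls the density marginal and draws σ² first.

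The missing hat on θ may be a PDF reading error, since Greek symbols are misread elsewhere in this part of the text; the discount weight, for example, appears as θ̂ at the start of the Combine step. That weakens any charge of circularity. It does not explain the absent determinant.

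The SAP also does not claim an error rate of 0.025. It reports a simulated 0.038 for the whole procedure. If those simulations used the same sampler, which is likely but not stated, any effect is already inside that figure. The frequentist ANCOVA in section 9.9.6 does not use this density. These points stand, and they limit the matter to a minor one.

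**Conclusion.** The formula is wrong as a marginal posterior, and the missing |V_θ|^(1/2) is the firm part of the error. The practical effect is conditional and small. If the formula is programmed with θ̂, posterior SDs and 95% intervals are about 0.7–1.4% too small without borrowing and about 0.4–0.5% too small with full borrowing. Overall one-sided type I error rises by about 0.001 under the discounting that reproduces Table 4, and by about 0.002 with no borrowing (0.0519 − 0.0495 = 0.0024). Power is essentially unchanged.

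These sizes rest on Table 3's inputs, the assumed arm splits and null means, and the Weibull CDF reading of the discount function. Whether bayesDP v1.3.2 has the error is unknown from the documents. This is a minor specification error in the primary analysis.

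**What to change.** In section 9.9.4.1 replace the printed density with

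`q(σ² | y) ∝ π(σ²) · |σ² I_n|^(-1/2) · |V_θ|^(1/2) · exp{ -½ (y* - X*θ̂)' Σ*⁻¹ (y* - X*θ̂) }`,

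stating that θ̂ and V_θ are evaluated at each grid value of σ². Check that `bdplm` in bayesDP v1.3.2 samples from this density. Footnote 10 shows that the code has already been inspected once, so a second look is feasible.

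If the code differs, either correct the sampler or keep the locked version and state the small understatement of the intervals. If the code already matches, only the text changes. Otherwise the cost is the code check and, if the sampler is altered, renewed validation under section 10 and possibly a re-run of Table 4.
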